1.3 Overview of Clinical Studies

For more detail refer to the prescribing information for cytarabine.¹⁴

Historically, poor outcomes were reported when conventional doses of cytarabine were used as post-remission therapy in AML, so groups studied higher doses of cytarabine for post-remission therapy. The Cancer and Leukemia Group B (CALGB) compared various doses of cytarabine consolidation in AML patients in CR after induction therapy.⁷ Subjects in this trial were randomized into three groups (each planned to receive 4 cycles of consolidation of the following): 1.) 100 mg/m² continuous IV x 5 days, 2.) 400 mg/m² IV daily x 5 days or 3.) 3000 mg/m² IV q12h x 6 doses on Days 1, 3, and 5. These authors found that subjects who received high dose cytarabine were more likely to remain in CR and lived longer than patients who received lower doses of cytarabine. This trial was pivotal in establishing HiDAC as the standard post-remission/consolidation chemotherapy in the USA, as it was the first to show superior efficacy outcomes compared to anthracycline and conventional dose cytarabine for consolidation. Hematologic toxicity was main adverse effect, and 71% of patients were hospitalized due to infection or febrile neutropenia. Growth factors were not used in the trial. After excluding subjects over the age of 60 years after seeing higher rates of CNS toxicity (32%), severe CNS toxicity was recorded in 12% of subjects aged 60 years or younger.

However more than half of patients are diagnosed over the age of 60 years with lower rates of CR compared to younger patients, so Sperr and colleagues designed a trial evaluating lower doses of cytarabine as consolidation chemotherapy in elderly AML subjects in CR.⁸ In this trial, patients received up to four cycles of cytarabine 1000 mg/m² IV q12h on Days 1, 3, and 5. Prophylactic growth factor was not routinely used. Neutropenic fever was recorded in 44-72% of cycles. No severe CNS adverse effects were reported. Drug fever was seen in 32% and rash occurred in 17% of cycles. The results of this trial demonstrated that elderly AML patients can tolerate attenuated doses of HiDAC, which became the standard consolidation regimen for many institutions in the US.

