2.2.2 Secondary endpoint(s)

- To determine the safety of HiDAC 123 compared to standard HiDAC 135 in case controls by evaluating the differences in:
 - duration of neutropenia and thrombocytopenia (see neutropenia definition above). Thrombocytopenia is defined as the interval between the first day of platelets < 50x10³/uL after consolidation chemotherapy to the first day of recovery (defined as first day of platelets > 20x10³/uL if consecutive x 2 and not transfused)
 - incidence of documented infections (bloodstream infection (BSI), pneumonia, invasive fungal infection (IFI), Clostridium difficile infection (CDI), typhlitis, (see Appendix A) and rates of febrile neutropenia (defined as temperature \geq 38.3 C° once or \geq 38 C° for more than 1 hour and ANC less than 500/mm³ or expected to fall below 500/mm³ in next 48 hours)
 - number of RBC and platelet transfusions given per cycle will be recorded in units
 - readmission rates (incidence and reason for admission) and LOS recorded in days (total, including chemotherapy administration, and readmission days)
 - non-hematologic toxicity: focus on CNS/cerebellar and ocular as these are specific to high dose cytarabine, but will record incidences of any other grade 3-5 organ systems according to CTCAE v5 criteria
 - time to next treatment (next chemotherapy cycle, transplant, etc.; if chemotherapy was discontinued prior to planned date, what was the reason)

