4.3 Exclusion Criteria

Subjects with any of the following will not be eligible for study participation:

- A. Age < 61 years
- B. Patients unable to provide informed consent for prospective arm
- C. Secondary AML (*documented* history of antecedent hematological disorder, e.g., myelodysplastic syndrome or therapy-related AML) or CML in blast crisis
- D. Patients receiving, received, or who will receive a FLT3 inhibitor
- E. Patients receiving, received, or who will receive an IDH1 or IDH2 inhibitor
- F. SCr greater than 2 mg/dL
- G. Karnofsky PS of 40 or less at study entry
- H. History of any other disease, metabolic dysfunction, physical examination finding, or clinical laboratory finding giving reasonable suspicion of a disease or condition that contraindicates the use of protocol therapy or that might affect the interpretation of the results of the study or that puts the subject at high risk for treatment complications, in the opinion of the treating physician
- I. Prisoners or subjects who are involuntarily incarcerated, or subjects who are compulsorily detained for treatment of either a psychiatric or physical illness

J. For historical arm, subjects will be excluded if adequate data is not available in electronic medical record (e.g., if patient was followed by their local oncologist between chemotherapy cycles and labs/transfusions/clinic notes, etc. are not available)

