7.3.5 Hematopoietic Stem Cell Transplantation Treatment

Subjects may undergo allogeneic stem cell transplant after study entry; at the start time of conditioning therapy, the subject will be removed from the study. The time to next treatment (date of conditioning) will be recorded. The conditioning regimen, donor type and graft source during the allogeneic HCT period will be recorded.

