12.3 Analysis of Primary Endpoint

When the required assumptions are met, duration of neutropenia will be analyzed by a one-sided, two sample, equal-variance t-test. If the normal distribution and equal variance are not validated, the corresponding non-parametric method will be used. Primary analysis will be for cycle 1 of consolidation only. Other cycles will be recorded and use descriptive statistics. Further, multivariable linear regression model of the neutropenia in days with group as the primary independent variable of interest will be fitted, while adjusting for some potential confounding variables, including AML type (WHO and FAB), documented infection in consolidation #1 (yes or no), ELN risk category (favorable, intermediate, high) and MRD positivity (yes or no), WBC at diagnosis (<50,000 or \geq 50,000), delay between induction course and consolidation #1 (less than or more than 40 days), allogeneic HCT (yes or no).

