Probable IFI²⁴ Subjects MUST have one each (at a minimum) of host, clinical, and microbiologic criteria	
Host criteria:
 
 Recent history of neutropenia (< 500 cells/mm³ for > 10 days) temporally related to onset of fungal disease; OR Received an allogeneic HSCT; OR Corticosteroid use for > 3 weeks (average dose 0.3 mg/kg/d prednisone equivalent); OR Treatment with T-cell immune suppressants (e.g., cyclosporine, TNFα blocker, specific monoclonal antibodies or nucleoside analogues) within the last 90 days; OR Inherited severe immunodeficiency; 
Clinical criteria:
 
 Lower respiratory tract fungal disease (1 of 3 on CT scan): 
 Dense, well circumscribed lesion(s) with or without a halo sign; OR 	
Microbiologic criteria
 
 Mold in sputum, BAL fluid, bronchial brush, or sinus aspirate samples, indicated by 1 of either presence of fungal elements indicating a mold or recovery of a mold by culture (e.g., Aspergillus, Fusarium, Zygomycetes, or Scedosporium spp.); OR Positive evidence of GM in serum, BAL or CSF; OR Positive evidence of β-D-glucan in serum

Type of Infection	Clinical/Radiographic Criteria	Laboratory/Microbiological
	
 ○ Air-crescent sign; OR ○ Cavity; OR • Tracheobronchitis (mark the finding(s) per bronchoscopic evaluation) 
 ○ Tracheobronchial ulceration; OR ○ Nodule; OR ○ Pseudo-membrane; OR ○ Plaque or eschar; OR • Sinonasal Infection (imaging showing sinusitis plus 1 of the following 3 signs): 
 ○ Acute localized pain (including pain radiating to the eye); OR ○ Nasal ulcer with black eschar; OR ○ Extension of the paranasal sinus process across bony barriers; OR • CNS Infection (1 of the following): 
 ○ Focal lesions on imaging; OR ○ Meningeal enhancement on MRI or CT; 	

Type of Infection	Clinical/Radiographic Criteria	Laboratory/Microbiological
	
OR
 
 • Disseminated candidiasis (at least 1 of the followings after an episode of candidemia within the previous 2 weeks): 
 ◦ Small target-like abscesses (bull's eye lesions) in liver or spleen; OR ◦ Progressive retinal exudates on ophthalmologic examination 	

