Clostridium difficile infection (CDI)²⁵ Diagnosis will be if the clinical criterion is met AND there is microbiological confirmation	Presence of at least 3 unformed bowel movements in a 24-hour period or fewer consecutive hours	
 • A stool test result positive for the presence of toxigenic C. difficile or its toxins or colonoscopic OR histopathologic findings demonstrating pseudomembranous colitis • Patients presenting with ileus or megacolon will need a perianal specimen test positive for C. difficile or its toxins
Typhilitis²⁶ Diagnosis will be if the clinical criteria are met AND there is microbiological confirmation	
 • Patients with fever > 38.3°C * or > 38°C sustained for 1 hour, neutropenia and abdominal signs such as abdominal cramping, abdominal pain (> 3 on VAS), abdominal distention, diarrhea, GI bleeding AND • Exclusion of other diagnoses such as C. difficile associated colitis or other biopsy proven diagnosis 	
 • ANC ≤ 500/mm³ AND • Bowel wall thickening on CT exam or US exam > 4 mm (transverse scan) thickening in any segment of the bowel for at least 30 mm length (longitudinal scan)

Type of Infection	Clinical/Radiographic Criteria	Laboratory/Microbiological
	*Fever may be absent in a minority of patients and some may even be hypothermic.	
Other Infections		
Febrile Neutropenia²⁷ Both clinical and laboratory criteria should be met	
 • A single oral temperature of $> 38.3^{\circ}\text{C}$ (101°F) OR • A temperature of $> 38.0^{\circ}\text{C}$ (100.4°F) sustained for > 1 hour 	
 • ANC < 500 cells/mm^3 OR • ANC that is expected to decrease to < 500 cells/mm^3 during the next 48 hours
Upper RVI²³	
 • No new pulmonary infiltrates per CT chest or chest X-ray • Symptoms of upper respiratory tract infection 	Respiratory virus detected in a nasopharyngeal swab or sputum by multiplex-PCR
Possible Lower RVI²³	New pulmonary infiltrates per CT chest or chest X-ray (but without confirmation of respiratory virus in the lower respiratory tract) with or without LRTD signs or symptoms (e.g., cough, wheezing, rales, tachypnea, shortness of breath, dyspnea, or hypoxia).	Respiratory virus detected in a nasopharyngeal swab or sputum by multiplex-PCR

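### The supplementary regression in Section 12.3 adjusts cycle-1 neutropenia for infection in consolidation 1 and for allogeneic HCT, which both arise after treatment starts and are not confounders

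*Combined protocol and SAP*

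**What the plan says.** Section 12.3 restricts the primary analysis to cycle 1 and tests it with a one-sided, two-sample t-test. It then adds a multivariable linear regression of neutropenia days with group as the variable of interest, "adjusting for some potential confounding variables, including AML type (WHO and FAB), documented infection in consolidation #1 (yes or no". The list goes on to ELN risk, MRD, WBC at diagnosis, "delay between induction course and consolidation #1 (less than or more than 40 days), allogeneic HCT (yes or no".

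Elsewhere the documents treat these two variables as results of treatment:

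- Section 2.2.2 makes infection a secondary endpoint compared between schedules: "incidence of documented infections (bloodstream infection (BSI), pneumonia, invasive fungal infection (IFI".
- The synopsis rationale names fewer infections as a possible benefit of the new schedule, and Section 1 describes infection as a toxicity that goes with marrow suppression.
- In Appendix A, typhlitis requires "neutropenia and abdominal signs such as abdominal cramping" together with ANC at or below 500/mm³. One host criterion for probable invasive fungal infection is "Recent history of neutropenia (< 500 cells/mm³ for > 10 days) temporally related to onset of fungal disease".
- Section 7.3.5 places HCT later: "Subjects may undergo allogeneic stem cell transplant after study entry". The subject leaves the study at conditioning, and Section 2.2.2 counts transplant under time to next treatment.

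**The concern.** A confounder must precede treatment, or share a cause with it, and must also affect the outcome. Infection during cycle 1 comes after treatment and is driven at least partly by how long neutropenia lasts. Adjusting for it conditions the outcome on its own consequence. If infection instead prolongs neutropenia, it is a mediator, and adjusting for it removes part of the effect that Section 12.2 sets out to show. HCT after cycle-1 recovery can influence neither the schedule given nor a duration that has already ended.

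Controls are historical and matched only on age, sex, Karnofsky status and number of HiDAC cycles. The regression is therefore the one planned check on imbalance in ELN risk, MRD, WBC and induction-to-consolidation delay. Readers will use its group coefficient to judge whether the t-test result survives adjustment. As specified, it can disagree with the t-test for reasons unrelated to confounding.

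**Working it through.** **1. Inputs.** From Section 12.2: means of 19 and 16 days, SD 4, 23 evaluable per group, one-sided alpha 0.05, 20% dropout. The documents do not give the infection association, so it is assumed: prevalence 30, 50 or 70% (Section 1.3 offers only a related figure, "Neutropenic fever was recorded in 44-72% of cycles") and an odds ratio (OR) of 1.1 to 1.3 per extra neutropenic day.

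**2. The plan's own figures.** SE = 4 × √(2/23) = 1.18 days. Power is 80.5% from the exact noncentral t (44 df) and 81.6% by normal approximation, against 81% stated. Accrual is 23/0.80 = 28.75, so 29. Both figures reproduce. They concern the t-test; the plan gives none for the regression.

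**3. Timing of the listed covariates.**

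| Covariate | Known before cycle 1 Day 1? |
|---|---|
| AML type, ELN risk, WBC at diagnosis | Yes |
| MRD (assessed before study entry, Section 2.3.2) | Yes |
| Induction-to-consolidation delay | Yes |
| Infection in consolidation 1 | No |
| Allogeneic HCT | No |

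**4. Infection as a consequence of duration.** The model is D = 19 − 3G + N(0, SD 4), with logit P(infection) = a + ln(OR) × (D − 17.5) and a set to give the stated prevalence. D is then regressed on G (1 = HiDAC 123) and infection. In least squares,

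adjusted coefficient = crude difference − b × (infection proportion in 123 − proportion in 135),

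where b is the within-group difference in days between infected and uninfected subjects. At OR 1.3 and 50% prevalence the proportions are 42% and 58% and b is about 3.4 days, so −3.0 − 3.4 × (0.42 − 0.58) = −2.46. Large-sample simulation over the grid (error about 0.02 days) gives:

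| Prevalence | OR 1.1 | OR 1.15 | OR 1.2 | OR 1.3 |
|---|---|---|---|---|
| 30% | −2.91 | −2.83 | −2.72 | −2.52 |
| 50% | −2.90 | −2.79 | −2.68 | −2.46 |
| 70% | −2.93 | −2.82 | −2.73 | −2.52 |

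That is 2% (0.07/3) to 18% (0.54/3) toward zero.

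**5. Trial level** (23 per group, 20,000 simulated trials per scenario). With a true effect of −3, the t-test has 80-81% power and the adjusted test 71-79%. In 3.4-11.5% of trials the t-test is significant and the adjusted test is not. With no true effect, the adjusted test rejects in 4.9-5.2%, so under this mechanism alone the error is conservative.

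**6. Recording that differs by cohort.** Controls come from chart review, while Section 11.1.1 has prospective subjects assessed in hospital and at every visit. Let infection at equal duration differ by an assumed OR c (123 versus 135), with a true effect of 0 and 50% prevalence:

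| c | Coefficient at OR 1.1 / 1.2 / 1.3 per day | One-sided rejection at nominal 5% |
|---|---|---|
| 2 | −0.24 / −0.40 / −0.48 | 7.2 / 9.9 / 11.4% |
| 0.5 | +0.24 / +0.40 / +0.48 | 3.1 / 2.3 / 1.6% |

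**7. Infection as mediator.** Suppose the schedule lowers infection from 50% to 30% and infection adds m days (all assumed). The adjusted coefficient is the direct effect, −3 + 0.2m: −2.8, −2.6 and −2.2 for m = 1, 2 and 4. The total effect is still −3.0.

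**8. HCT.** With HCT odds multiplied by 1, 0.95 or 0.9 per extra neutropenic day (assumed, base risk 40%), the coefficient is −3.00, −2.97 or −2.88. Adjustment removes no confounding here and at most adds a small distortion.

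**The case against.** - **The regression is supportive only.** It carries no alpha or decision rule, its covariate list is open-ended, and it could be refitted later from data already collected. This stands and limits the severity. A later refit, however, would choose covariates after the results are known.
- **The ANC-based definitions add little.** At the planning means and SD, about 93% and 99% of subjects would exceed 10 days of neutropenia, so the fungal host criterion hardly discriminates, and it is one of several alternatives. The definitions of bloodstream infection, pneumonia and *C. difficile* infection contain no ANC term. This also stands. The case rests on timing and causal order, not on the definitions.
- **The prevalence anchor is a different endpoint.** Febrile neutropenia is not documented infection, and the cited trial did not routinely use growth factor. At an assumed 10-20% prevalence the coefficient is about −2.95 to −2.6, so the bias shrinks but remains.
- **Adjustment could help.** If infection risk differed by calendar period for reasons other than schedule, and infection prolonged neutropenia, adjustment would remove bias. With infection adding 1-4 days and risks of 50% and 30% in either direction, the crude estimate would run from −3.8 to −2.2 and the adjusted one would be −3.0. The documents do not exclude this, but nothing in them establishes it. Their stated expectation is that the schedule itself may lower infection, and in that case adjustment removes real effect.
- **The 11.4% rejection rate is an extreme corner.** It needs an OR of 1.3 per day (about eightfold over eight days) and a twofold recording difference. Section 4.3 also narrows that difference: "For historical arm, subjects will be excluded if adequate data is not available in electronic medical record". This is fair; the figure bounds the range and is not a forecast.
- **HCT may stand in for baseline fitness or transplant intent.** If so, a variable recorded at entry would serve better than a later event.

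**Conclusion.** The covariate list is wrong as written. Two of its entries are post-treatment variables labelled as confounders, and with infection in the model the group coefficient does not in general estimate the schedule effect. That conclusion follows from the documents' own timing and needs no assumed odds ratio. The infection bias would vanish only if infection were unrelated to duration of neutropenia, contrary to the protocol's rationale.

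The size does rest on assumptions. The likely effect is attenuation of 0.07 to 0.54 days out of 3.0, smaller than the 1.18-day standard error, with a loss of up to about 10 points of power. The direction is not guaranteed if infection recording differs between cohorts. For HCT no material bias is shown; it simply has no role in the model. The primary test and sample size stand. This should be fixed, but it does not threaten the trial.

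**What to change.** In Section 12.3, delete documented infection in consolidation 1 and allogeneic HCT from the covariate list. State that adjustment is limited to variables known before Day 1 of cycle 1: AML type, ELN risk, pre-entry MRD, WBC at diagnosis and induction-to-consolidation delay, all of which are already listed. Age, sex and Karnofsky status may be added for imbalance left after matching. The fourth matching factor, number of HiDAC cycles, should stay out because it is known only after cycle 1. Report infection and HCT as outcomes, as Section 2.2.2 already provides.

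The cost is one sentence of wording. It needs no new data and no change to the sample size or to patient care.

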12.2 Sample Size Justification

This is a prospective single group study to determine the duration of neutropenia after consolidation chemotherapy with HiDAC 123. A historical control group will be selected by identifying patients who received cytarabine 1000 mg/m² IV q12h D135 from 2/1/2017-

2/1/2019 by propensity matching factors: age (+/- 3 years), gender (male or female), Karnofsky PS (90-100/70-80/50-60), and number of HiDAC cycles. The hypothesis is that patients with HiDAC123 treatment schema have a shorter duration of neutropenia after consolidation chemotherapy, compared to matched historical controls who received HiDAC 135. Group sample sizes of 23 subjects from a prospective cohort and 23 subjects from historical baseline group will achieve 81% statistical power to reject the null hypothesis of equal means when the population mean difference in neutropenia duration is three days (16 vs. 19 days) with a standard deviation for both groups of four days and statistical significance level (alpha) of 0.05 using a one-sided, two sample, equal-variance t-test. Including 20% drop out rate, we will accrue 29 subjects per cohort.

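### The supportive regression in 12.3 cuts delay and white cell count in two and spends an unstated number of terms on WHO, FAB and ELN classes; a closed list of baseline covariates would control confounding better.

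*Combined protocol and SAP*

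**What the plan says.** Section 12.3 makes the cycle 1 comparison primary: when assumptions hold, "duration of neutropenia will be analyzed by a one-sided, two sample, equal-variance t-test", and otherwise a non-parametric counterpart. It then adds a multivariable linear regression of neutropenia days, with group as the term of interest, adjusting for some potential confounders. The named ones are:

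- AML type: "including AML type (WHO and FAB"). No class counts and no rule for sparse classes are given.
- Documented infection in consolidation #1 (yes or no).
- ELN risk in three categories, and MRD positivity.
- White cell count: "WBC at diagnosis (<50,000 or \geq 50,000").
- Delay: "delay between induction course and consolidation #1 (less than or more than 40 days").
- Allogeneic transplant (yes or no).

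The list is introduced as examples, so it is not closed. Section 12.2 sizes the study on the unadjusted test alone.

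**The concern.** The design is non-randomised, with controls treated between February 2017 and February 2019. Matching covers age within 3 years, gender, Karnofsky band and number of cycles. The regression is the only planned check that a difference in neutropenia is not due to other differences between the cohorts, so how it handles confounders matters.

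There are three weaknesses. WHO type, FAB type and ELN category all classify the same leukaemia, and the first two use an unknown number of terms in a small data set. Delay and white cell count must be known as numbers before they can be cut, and cutting them discards part of what adjustment is meant to remove. A delay of exactly 40 days also falls in neither group. Finally, infection in consolidation #1 and allogeneic transplant arise after treatment starts, so adjusting for them can bias the schedule effect.

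**Working it through.** **Inputs from 12.2.** "23 subjects from historical baseline group will achieve 81% statistical power"; "population mean difference in neutropenia duration is three days (16 vs. 19 days"); "with a standard deviation for both groups of four days"; "statistical significance level (alpha) of 0.05 using a one-sided, two sample, equal-variance t-test".

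**The plan's own figure.** SE = 4 × √(2/23) = 1.18 days. The non-centrality is 3/1.18 = 2.54 on 44 df, and one-sided power at 0.05 is 80.5% (81.6% by the normal approximation). This reproduces the stated 81%. Accrual: 23/0.8 = 28.75, so 29 per cohort, as stated.

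**Counting covariate df.** The text fixes ELN 2 + infection 1 + MRD 1 + white cell count 1 + delay 1 + transplant 1 = 7. WHO and FAB levels are not given. If both are entered, I assume FAB takes 1 to 6 df (at most seven classes without M3) and WHO 1 to 4 (at most five classes). The total is then 9 to 17.

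**Precision of the group effect.** Let N = 46 and let k be the number of covariate df, with covariates unrelated to group. The average variance inflation is (N − 3)/(N − 3 − k), and residual df are N − 2 − k.

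- k = 9: 43/34 = 1.26; 1.18 × √1.26 ≈ 1.32.
- k = 17: 43/26 = 1.65; 1.18 × √1.65 ≈ 1.5.

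Averaging non-central t power over the random inflation, with covariates that explain none of the outcome, gives:

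| Model | Covariate df | Residual df | SE (days) | Power for 3 days |
|---|---|---|---|---|
| Unadjusted | 0 | 44 | 1.18 | 80.5% |
| Text without WHO and FAB | 7 | 37 | 1.28 | 74% |
| Text, few classes | 9 | 35 | 1.32 | 72% |
| Text, many classes | 17 | 27 | 1.5 | 62% |
| Proposed list | 8 | 36 | 1.31 | 73% |

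At 17 df the 95% half-width is about 3.1 days, against 2.4 unadjusted and a target difference of 3.

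**Sensitivity at 17 df.** If the covariates explain 20% of the outcome variance, power is about 70%; at 40% it is about 80%, level with the unadjusted test. If all 58 accrued subjects are evaluable and the covariates explain nothing, the SE is 1.25 and power 76% (unadjusted: 1.05 and 88%). Imbalance between the cohorts would raise the SE; this is not modelled.

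**Class overlap.** I compared simulated categorical covariates with seven FAB, five WHO and three ELN levels (assumed prevalences), with and without WHO partly determined by ELN. The SE was 1.45 with overlap and 1.48 without.

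**Cost of the cuts.** Take a normal confounder with a linear effect on the outcome, shifted between cohorts by 0.3 to 0.8 SD. Adjusting for a median split leaves about 36% of the confounding bias in the group effect, and adjusting for a split at the upper 20% leaves about 52–54%. A correctly specified linear term leaves none. A binary term and a linear term each cost 1 df. The documents do not say where 40 days or 50,000 falls in this population, so these figures show a range.

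**The case against.** The regression is a further analysis. The t-test is primary, and no power claim or decision rests on the adjusted model. This stands, and it limits the point to an improvement.

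The 17 df are an assumption. The text could mean one collapsed AML-type variable, and restriction to de novo, non-M3 disease reduces the possible classes. This also stands: 17 is the top of an assumed range.

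Age, gender and Karnofsky are handled by matching, and an open list does not exclude them. This stands in part. Age is matched only within 3 years, and the primary test is unpaired. Adding age and Karnofsky group is reasonable but is not where the main gain lies.

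Two further inferences are tempting and do not hold. A reader might infer that overlap among WHO, FAB and ELN inflates the uncertainty of the group effect. It destabilises the coefficients of those classes, but the simulation shows no inflation of the group SE. A reader might also take delay to be the factor most related to marrow recovery. The documents do not say so; section 1.3 names age, prior treatment and antecedent haematologic disorder among the factors affecting recovery.

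**Conclusion.** The point holds as a cheap improvement. The adjusted model is under-specified. If covariates explain nothing and are unrelated to group, its SE is about 12% (1.32/1.18) to 27% (1.5/1.18) wider than the unadjusted one for 9 to 17 df, and power falls from 80.5% to between 72% and 62%. Cutting delay and white cell count costs control of confounding, not precision of the group effect. Under a normal, linear confounder, about a third to a half of the bias can remain.

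A reader might conclude that the adjusted effect is too imprecise to use. The documents do not support that: only 7 df are fixed by the text, the worst case needs covariates with no prognostic value, and the loss is gone if they explain about 40% of the variance.

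**What to change.** In 12.3, replace the open list with a closed one, fixed before analysis: ELN category (2 df), MRD (1), days from induction to consolidation #1 as continuous (1), log white cell count at diagnosis as continuous (1), age (1) and Karnofsky group (2). The total is 8 df, with SE about 1.31 and power about 73% under the same assumptions.

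Drop WHO and FAB type in favour of ELN category. Leave out infection in consolidation #1 and allogeneic transplant, because both arise after treatment starts. Dropping WHO and FAB alone, while keeping those two and adding age and Karnofsky group, would leave 7 + 1 + 2 = 10 df, SE about 1.34 and power about 71%, and would retain the post-treatment terms.

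The gain is mainly in confounding control and a settled specification, since precision is close to that of the 9 df reading. Continuous delay also removes the gap at exactly 40 days.

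The cost is a change of wording. Age and Karnofsky are already needed for matching, and delay and white cell count are needed as numbers before they can be cut. The small downsides are that morphologic subtype is no longer adjusted for and that linearity of the continuous terms is assumed.
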